The protocol, informed consent form(s), recruitment materials, and all participant materials will be submitted to the Institutional Review Board (IRB) for review and approval. Approval of both the protocol and the consent form must be obtained before any participant is enrolled. Any amendment to the protocol will require review and approval by the IRB before the changes are implemented to the study. In addition, all changes to the consent form will be IRB-approved; a determination will be made regarding whether a new consent needs to be obtained from participants who provided consent, using a previously approved consent form.

1 PROTOCOL SUMMARY

1.1 SYNOPSIS

Title:	A Phase 1 Dose Escalation Trial Evaluating the Safety and Pharmacokinetic Profile of BIO 300 Oral Powder in Healthy Volunteers
Study Description:	
Single Ascending Dose:
 
Open-label, single-dose escalation in healthy volunteers. Each cohort will enroll 8 subjects of which 2 will be backups (1M/1F), so that at least 6 subjects (3M/3F) complete the protocol procedures. The pertinent safety data will be reviewed for each cohort before the next dose level cohort is started. Subjects will follow a diet low in soy isoflavones for 7 days before and 7 days after treatment and will fast at least 8 h before dosing. The test article will be administered on day 1 and the initial dose will be one BIO 300 Oral Powder sachet, 500 mg genistein. Subsequent doses will be 2x the previous cohort. The fourth, and final cohort, dose level will be TBD based on the safety and pharmacokinetic (PK) results from the previous 3 cohorts. Subjects will remain in the clinic 12 hours after dosing for observations and blood sample collection for clinical lab assessment, PK, and pharmacodynamics (PD). Subjects will remain fasted for 4 hours after the test article administration. Subjects will be provided a standardized low soy meal after the 4-hour blood draw and after the 8-hour blood draw. Subjects will return to the clinic on day 2, 3 and 8 after dosing for blood sampling and/or observations as detailed in the schedule of events. Subjects may not miss any clinic visits. At the conclusion of the study, data will be analyzed from all cohorts to determine safety and PK. PD samples will be stored until the completion of all phase 1 studies, and then sent for RNA sequencing and data analysis.

Multiple Single Dose:

Open-label, single dose given daily for 6 days in healthy volunteers. A single cohort will enroll 14 subjects (7M/7F) of which 4 will be backups (2M/2F), so that at least 8 subjects (4M/4F) complete the protocol procedures. Subjects will follow a diet low in soy isoflavones for 7 days before treatment, during the 6 days of treatment and 7 days after treatment. Subjects will fast at least 8 h before the first dose, 3rd dose and the 6th dose. The test article will be administered starting on day 1 and the dose used in this study will be determined based on safety and PK analysis from the single ascending dose study. Subjects will be administered test article daily during their schedule clinic visits. Subjects will remain in the clinic 4 hours after the first dose and 12 hours after the 6th dose for observations and blood sample collection for clinical lab assessment, PK and PD. Subjects will remain fasted for 4 hours after the test article administration on days 1 and 6. On the 6th day, subjects will be provided a standardized low soy meal after the 4-hour blood draw and after the 8-hour blood draw. Blood sampling and/or observations will be performed on dosing days 1-6 as described in the schedule of events. Subjects will return to the clinic on days 7, 8 and 13 after initial dosing for blood sampling and/or observations as detailed in the schedule of events. Subjects may not miss any clinic visits. At the conclusion of the study, data will be analyzed to determine safety and PK, and data will be analyzed from all cohorts to determine PD.

Objectives:

Primary Objectives:

- Determine the overall adverse event and PK profiles of single ascending doses of BIO 300 Oral Powder in healthy volunteers
- Determine the overall adverse event and PK profile of multiple doses of BIO 300 Oral Powder in healthy volunteers

Secondary Objectives:

- Determine the effects of single and multiple doses of BIO 300 Oral Powder on blood-based biomarkers
- Use a combination of the PK and PD profiles from the single and multiple doses of BIO 300 Oral powder to identify the putative BIO 300 Oral Powder human efficacious dose

Endpoints:

Primary

Evaluate the safety and pharmacokinetics of BIO 300 Oral Powder in Healthy Volunteers

Secondary

Characterize the expression of blood-based biomarkers

Study Population:

[figure not shown]
- 6 subjects/cohort (3M/3F) will be recruited for the single ascending dose study, and at least 6 (3M/3F) subjects/cohort will complete all aspects of the study. 2 additional subjects (1M/1F),

[figure not shown]
will be screened, consented and available as backups for each cohort.

- 10 (5M/5F) subjects will be recruited for the multiple single dose study, and at least 8 (4M/4F) subjects will complete all aspects of the study. 4 additional subjects (2M/2F) will be screened, consented and available as backups.
- In total, at least 32 healthy volunteers who will complete all aspects of the trial.

Phase:	1
Description of Sites/Facilities Enrolling Participants:	Nucleus Network (formally Prism Clinical Research) [name]
Description of Study Intervention:	BIO 300 Oral Powder will be provided by Humanetics Corporation, Minneapolis, Minnesota. [REDACTED] [REDACTED] The inactive ingredients include povidone K12 and sucralose powder. The vials are labeled with clinical study information including the lot number, storage instructions to store at controlled room temperature 15-30°C (59-86°F) and the statement "CAUTION: New Drug, limited by Federal law to investigational use."
Study Duration:	Approximately 8 months
Participant Duration:	The duration of study participation will be 35 days for Cohorts 1 – 4 (28-day screening period; Dosing on day 1; final follow-up visit on Day 8). The duration of study participation will be 41 days for Cohort 5 (28-day screening period; Dosing on days 1 - 6; final follow-up visit on day 13)

1.2 SCHEMA

1.3 SCHEDULE OF ACTIVITIES (SOA)

Schedule of Events and Assessments														
Visit Number	Single Ascending Dose Cohorts					Multiple Single Dose Cohort								
	1	2	3	4	5	1	2	3	4	5-6	7	8	9	10
Day	-28 to -8	1	2	3	8	-28 to -8	1	2	3	4-5	6	7	8	13
Informed Consent	X					X								
Medical History	X					X								
Concomitant Medication	X	X	X	X	X	X	X	X	X	X	X	X	X	X
Contraception Check	X	X	X	X	X	X	X	X	X	X	X	X	X	X
Vital Signs ¹	X	X ⁸	X	X	X	X	X ¹⁷	X	X	X	X ⁸	X	X	X
Calculation of BMI	X					X								
Physical Exam ²	X			X	X	X			X		X			X
Drug Screen/Alcohol Testing	X	X				X	X							
Pregnancy test ³	X	X				X	X	X						X
Hepatitis and HIV testing	X					X								
CBC with differential ⁴	X			X	X	X			X		X			X
PT/INR, PTT	X			X	X	X			X		X			X
Serum chemistries and fasting lipid panel ⁵	X			X	X	X			X		X			X
Urinalysis ⁶	X					X	X					X		X
ECG ⁷	X	X ⁹	X	X	X	X	X ⁹	X	X		X			X
Low isoflavone dietary counseling	X	X	X	X		X	X	X	X			X		
Administer BIO 300 Oral Powder		X					X	X	X		X	X		
PK		X ¹⁰	X ¹¹	X ¹²			X ¹³				X ¹⁰	X ¹¹	X ¹²	
PD		X ¹⁴	X ¹⁵				X ¹⁴				X ¹⁶	X ¹⁵		
Adverse Event Monitoring		X	X	X	X		X	X	X	X	X	X	X	X

Notes

1. Vital signs include height, weight, BMI, resting pulse, blood pressure, respiratory rate, and temperature. Subjects should be rested semi-recumbent for at least 5 min prior to collection.
2. Physical exams will assess the HEENT, lymphatic, cardiovascular, pulmonary, gastrointestinal, musculoskeletal, and neurological systems, and anything else deemed necessary by the Investigator.
3. Pregnancy test may be performed on urine or serum
4. CBC to include white blood cell count with differential, platelet count, red blood cell count, hemoglobin, and hematocrit
5. Serum chemistries to include total protein, albumin, sodium, potassium, chloride, bicarbonate, glucose, BUN, creatinine, alkaline phosphatase, ALT, AST, uric acid, LDH, total and direct bilirubin, phosphorous, calcium, magnesium, amylase, lipase, total cholesterol, triglycerides, HDL. Subjects should fast at least 8 h prior to collection and blood will be drawn prior to test article administration.
6. Urinalysis to include pH, specific gravity, dipstick determinations of protein, glucose, ketones, blood and bilirubin and reflex microscopic exam (reflex only if any qualitative measurements or appearance return abnormal)
7. ECGs to be performed in triplicate with 5-minute intervals. Subjects should be rested supine for at least 5 minutes prior to collection.

8. Vital signs to be obtained within 1 hour prior to administration of BIO 300 Oral Powder and then approximately 30 minutes, 1, 2, 4, 6, 8, and 12 h following administration of BIO 300 Oral Powder
9. ECGs to be obtained within 1 h prior to BIO 300 Oral Powder administration and then approximately 1, 2, and 4 h following BIO 300 Oral Powder administration
10. Samples for PK assessment to be obtained just prior to BIO 300 Oral Powder administration and then 30 minutes, 1, 2, 4, 6, 8, and 12 h following BIO 300 Oral Powder administration. The time of the blood draw will be ± 10 minutes of the nominal time.
11. Samples for PK assessment to be obtained 24 ± 2 h following administration of BIO 300 Oral Powder
12. Samples for PK assessment to be obtained 48 ± 4 h following administration of BIO 300 Oral Powder
13. Samples for PK assessment to be obtained just prior to administration of BIO 300 Oral Powder and then 30 minutes, 1, 2, and 4 h following BIO 300 Oral Powder administration. The time of the blood draw will be ± 10 minutes of the nominal time.
14. Samples for PD assessment to be obtained -2 to 0 h before BIO 300 Oral Powder administration, and 1, 2, and 4 h following BIO 300 Oral Powder administration. The time of the blood draw will be ± 10 minutes of the nominal time.
15. Samples for PD assessment to be obtained 24 ± 2 h following administration of BIO 300 Oral Powder
16. Samples for PD assessment to be -2 to 0 h before BIO 300 Oral Powder administration, and 4, 8, and 12 h following BIO 300 Oral Powder administration. The time of the blood draw will be ± 10 minutes of the nominal time.
17. Vital signs to be obtained within 1 hour prior to administration of BIO 300 Oral Powder and then approximately 30 minutes, 1, 2, and 4 h following administration of BIO 300 Oral Powder

2 INTRODUCTION

2.1 BACKGROUND AND STUDY RATIONALE

The active ingredient in BIO 300 Oral Powder is genistein, a selective agonist of estrogen receptor beta (ER β). ER β activation promotes DNA repair, cell cycle regulation, and importantly, anti-inflammatory effects. This pleiotropic mechanism can partly be explained by ER β 's ability to repress expression and activation of nuclear factor kappa light-chain-enhancer of activated B cells (NF- κ B), which is a master regulator that controls transcription of genes involved in the immune response and cell survival ¹⁻³. NF- κ B is activated in response to radiation, infection or other immune stimuli, and in turn promotes expression of pro-inflammatory cytokines [reviewed in ⁴].

Humanetics is developing BIO 300 for multiple clinical indications related to DNA damage and inflammation. The primary indication for BIO 300 Oral Powder is as a prophylactic medical countermeasure to increase survival in individuals exposed to myelosuppressive doses of ionizing radiation.

BIO 300 has been studied in a previous clinical trial (NCT02567799) as an aqueous oral nanosuspension (BIO 300 Oral Suspension). BIO 300 Oral Powder has been developed to facilitate a solid dosage form of BIO 300. The pharmacokinetics of BIO 300 Oral Powder are not fully known in humans, and the safety and maximum tolerated dose of this formulation is unknown. This phase 1 study is intended to methodically explore both safety and PK of this formulation in healthy human volunteers. In addition, blood-based biomarkers will be examined as part of an effort to develop a human dose conversion strategy under the FDA Animal Rule.

Refer to the Investigator's Brochure (IB) for more detail.

2.2 RISK/BENEFIT ASSESSMENT

[figure not shown]
2.2.1 KNOWN POTENTIAL RISKS

All study participants in this clinical trial will receive identical care and health assessments. This will be explained in detail at the time of consent to participate. Patient alternatives include the choice not to participate in this study, a decision that may mean no specific follow-up care.

Subjects with documented soy allergies should carefully consider taking BIO 300. Because BIO 300 is manufactured with synthetic genistein the risk of a soy-based allergic reaction is minimal. Although teratology studies were negative, it is not known if BIO 300 will cause harm when administered to pregnant women. If a patient becomes pregnant while taking BIO 300, the patient should be informed of potential hazards to the unborn fetus. For these reasons mothers who are nursing their children should be informed of potential hazards of taking BIO 300.

The following list summarizes the potential physical risks associated with participation in the proposed clinical study based upon known adverse events in previous clinical studies of BIO 300 at the proposed dose and dosing duration:

Less Likely

- Fatigue
- Constipation
- Diarrhea
- Dyspepsia
- Flatulence
- Anorexia
- Dysgeusia
- Increase in serum amylase
- Increase in serum lipase
- Decrease in the number of red blood cells
- Increase in blood pressure
- Lowering of the heart rate
- Increase in breathing rate
- Pain such as headaches, aches in muscles and joints and abdominal pain
- Change in appetite

- Bad taste in the mouth
- Breast changes like tenderness, enlargement, and discharge
- Change in menstrual cycle
- Fluid retention/swelling

Rare but serious

- Allergic reactions
- Increases in liver enzymes

2.2.2 KNOWN POTENTIAL BENEFITS

This is a phase 1 healthy volunteer study. There are no proposed benefits to the volunteers other than to participate in clinical research of an investigational drug.

2.2.3 ASSESSMENT OF POTENTIAL RISKS AND BENEFITS

BIO 300 and its active ingredient, genistein, have shown an exceptional safety profile in previous human use. The likelihood of serious adverse events associated with the ingestion of BIO 300 Oral Powder in this study is low. Subjects will be closely monitored for adverse events and will be evaluated through clinic visits during the dosing period of BIO 300 Oral Powder. Risks will be identified in the Informed Consent and clearly presented to volunteers prior to enrollment. Subjects are free to withdraw from the study at any time.

3 OBJECTIVES AND ENDPOINTS

OBJECTIVES	ENDPOINTS	JUSTIFICATION FOR ENDPOINTS
Primary Evaluate the safety and pharmacokinetics of BIO 300 Oral Powder in healthy volunteers.	
• Safety assessments including vital signs, clinical chemistries, ECG, and spontaneous reporting of adverse events.• Pharmacokinetic profile of four dose levels and profile after six days of repeated dosing	Phase 1 safety and PK analysis endpoints.

Secondary		
Characterize the expression of blood-based biomarkers	
Assessment of RNA changes related to single and multiple doses of BIO 300 Oral Powder.	Characterization of biomarkers relative to the mechanism of action that can be translated between species is a critical component of drug approval under the FDA Animal Rule.

4 STUDY DESIGN

4.1 OVERALL DESIGN

[figure not shown]
- Open label, single site phase 1 study in healthy volunteers who are equally distributed by sex.
- The study will include a single ascending dose (SAD) study in four cohorts and will be followed by a six-day multiple single dose study at either the highest dose or the maximum tolerated dose.
- There are no planned stratifications or sub-studies.

4.2 SCIENTIFIC RATIONALE FOR STUDY DESIGN

This study is designed as a traditional phase 1 in healthy volunteers.

4.3 JUSTIFICATION FOR DOSE

The starting dose of BIO 300 Oral Powder in the SAD study will be 500 mg API (1 BIO 300 Oral Powder sachet). This dose of BIO 300 Oral Powder is predicted to provide a drug exposure that is ≤ 0.5 times that of 1500 mg of BIO 300 Oral Suspension, which has a previous history of safety in a phase 1b/2a study. The predicted drug exposure for BIO 300 Oral Powder is based on the AUC and C_{max} achieved in nonhuman primate studies using two dose levels of BIO 300 Oral Powder. Extrapolating drug exposure in NHPs to humans assumed a linear dose-response relationship and used the recommended guidance from FDA for estimating the maximum safe starting dose in initial clinical trials for therapeutics in adult healthy volunteers.

4.4 END OF STUDY DEFINITION

The study will be considered completed at the last subject, last visit per the Schedule of Activities as defined in Section 1.3. Upon monitoring of all study data and locking of the database, the study site will be closed. Following the closing of the study site, the Sponsor will analyze the study data per the plan in

Section 9 and prepare a final study report that will be submitted to the Investigational New Drug Application (IND).

5 STUDY POPULATION

5.1 INCLUSION CRITERIA

In order to be eligible to participate in this study, an individual must meet all of the following criteria:

- 1) Healthy adult non-smokers, 18-64 years old.
- 2) BMI 18-32 kg/m²
- 3) No ingestion of prescription or over-the-counter medications (including dietary and herbal supplements) for 7 days prior to first dose of study drug and no planned use during study participation. Acetaminophen of up to 3 g/day and ibuprofen up to 1 g/day will be allowed at discretion of the Investigator.
- 4) At the discretion of the Investigator, blood routine, liver and kidney functions are within the controllable range.
 - a. Adequate hepatic function as evidenced by ALT, AST or LDH < 1.25X ULN and bilirubin < 1.5X ULN for the reference lab.
 - b. Adequate renal function as evidenced by a serum creatinine ≤ 1.5 X ULN for the reference laboratory OR a calculated creatinine clearance of ≥ 60 mL/min by the Cockcroft-Gault Equation.
 - c. Adequate hematopoietic function as evidenced by white blood cells ≥ 3x10⁹ / L and platelets ≥ 100x10⁹ / L.
- 5) Female subjects of childbearing potential must have a negative pregnancy test within 72 hours of the start of treatment.
- 6) Subjects must agree to abstain from heterosexual intercourse or use a reliable method of contraception for 7 days after their last dose. Subjects using hormonal contraception are required to utilize condom/spermicide + additional barrier method for 7 days after their last dose.
- 7) Ability to read and provide written informed consent.
- 8) Subjects who are willing and able to comply with all scheduled visits, treatment plan, laboratory tests, dietary restrictions, and other study procedures.
- 9) No clinically significant abnormalities identified by medical history, physical examination, vital signs, ECG, and clinical laboratory tests in the opinion of the Investigator.

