5.3 LIFESTYLE CONSIDERATIONS

Participants will be counseled to adhere to a low isoflavone diet, such as those listed in **Appendix 1**, during the dosing and PK/PD assessment period. It is important for study participants to maintain a low isoflavone diet (e.g., low soy-diet) in order to accurately quantify study drug pharmacokinetics and drug exposure.

Contraception:

- 1) Women who are not able to get pregnant are not required to use birth control. To be considered not able to get pregnant, you must be
 - a) postmenopausal for at least 12 months confirmed by hormone testing; **or**
 - b) surgically sterile
 - hysterectomy (surgical removal of uterus)
 - bilateral tubal ligation (tubes "tied")
 - removal of both ovaries and/or fallopian tubes
- 2) Women who are able to get pregnant must
 - a) have a negative urine pregnancy test at screening and on admission to CRU; **and**
 - b) must be using, and agree to continue using, an effective method of contraception for at least 4 weeks prior to first study drug administration until 7 days after the last dose of study drug.

Effective methods of contraception include the following:

- 1) Total abstinence from sexual intercourse with a partner that may result in pregnancy
- 2) Sexual intercourse with a partner who has had a vasectomy
- 3) Non-Hormonal Intrauterine device
- 4) Double barrier contraception, i.e., condom and diaphragm, or condom or diaphragm with spermicidal gel or foam.
- 5) Women using hormonal contraception below must agree to use a barrier or other effective method of contraception during the study
 - a) Combined (estrogen and progestogen containing) hormonal contraception
 - oral
 - intravaginal
 - transdermal
 - b) Progestogen-only hormonal contraception
 - oral
 - injectable
 - implantable

Women must not donate ova (eggs) during the study and for at least 30 days after the last dose of study drug.

Male subjects who have not had a vasectomy and/or subjects who have had a vasectomy but have not had 2 post-surgery negative tests for sperm whose partners are not on a highly effective method of contraception (hormonal contraception is sufficient for female partners) must agree to use an acceptable method of contraception from time of first dose of study drug until 30 days after the last dose of the study drug, and must not donate sperm during the study and for at least 30 days after the last dose of study drug.

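### Inclusion criterion 6 and protocol 5.3 give different contraception rules: 7 versus 30 days after the last dose for some men, and different barrier counts and periods for hormonal users

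*Combined protocol and SAP*

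**What the plan says.** **Criterion 6 (protocol 5.1).** All subjects agree to abstain or "use a reliable method of contraception for 7 days after their last dose". The next sentence adds: "Subjects using hormonal contraception are required to utilize condom/spermicide + additional barrier method for 7 days after their last dose". Neither sentence says when the obligation begins, and neither exempts anyone. Section 5.1 opens by stating that "an individual must meet all of the following criteria".

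**Section 5.3, men.** The rule covers men without a vasectomy and men with one who "have not had 2 post-surgery negative tests for sperm". A further condition on the partner limits it to those "whose partners are not on a highly effective method of contraception (hormonal contraception is sufficient for female partners"). They must agree to contraception from the first dose "until 30 days after the last dose of the study drug".

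**Section 5.3, women.** Those able to become pregnant need effective contraception from at least 4 weeks before the first dose until 7 days after the last. Those who cannot become pregnant are exempt. Under item 5 of the effective methods, hormonal users add one barrier, or some other effective method, for the duration of the study.

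**Elsewhere.** The Schedule of Activities (1.3) marks a contraception check at every visit, the last being Day 8 (single-dose cohorts) or Day 13 (multiple-dose cohort). Section 2.2.1 reports negative teratology studies but says that harm in pregnant women is not known.

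**The concern.** Both passages state what a subject must agree to, so both are operative instructions, and they differ on who is covered, for how long, and with how many barriers. No section says which prevails. Staff who screen from the criteria list would not ask the men covered by 5.3 for the 30-day commitment. Staff who counsel hormonal users from 5.3 would not mention the extra barrier that criterion 6 demands. What is at stake is participant protection and consistent eligibility decisions, not the estimate of any endpoint.

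**Working it through.** The plan gives no figure to reproduce. The check is a side-by-side reading plus day counts.

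| Element | Criterion 6 | Section 5.3 | Stricter |
|---|---|---|---|
| Men, end of period | 7 days after last dose | 30 days after last dose (subgroup) | 5.3 |
| Men, start | not stated | first dose | 5.3 |
| Women, end of period | 7 days after last dose | 7 days after last dose | same |
| Women, start | not stated | at least 4 weeks before first dose | 5.3 |
| Hormonal users, barriers | condom/spermicide plus a further barrier | one barrier, or another effective method | criterion 6 |
| Hormonal users, period | after last dose; start not stated | whole study, dosing days included | 5.3 |
| Women unable to conceive; men with confirmed vasectomy | included, as all subjects are | women exempt; men outside the rule | criterion 6 |

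**Gap for men in the 5.3 subgroup.** 30 − 7 = 23 days.

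- Single-dose cohorts: last dose on Day 1. Criterion 6 ends on 1 + 7 = Day 8; 5.3 ends on 1 + 30 = Day 31.
- Multiple-dose cohort: last dose on Day 6. Criterion 6 ends on 6 + 7 = Day 13; 5.3 ends on 6 + 30 = Day 36.

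Days 8 and 13 are also the final visits (synopsis, Participant Duration). The extra 23 days therefore begin when scheduled contact ends, and the instruction has to be given by then.

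**How many men.** From the synopsis (Study Population), 4 cohorts × 3 men + 5 men = 17 planned for dosing. If every backup is dosed, 4 × (3 + 1) + (5 + 2) = 23. The documents do not say how many would fall in the subgroup, so the range is 0 to 17, or 0 to 23 with backups. The version 2.0 rationale in section 10.3 draws on Cmax from all four single-dose cohorts, so a change to this version would mainly reach the multiple-dose cohort: 5 men, or 5 + 2 = 7 with backups.

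**Hormonal users.** The end dates coincide, because the study ends for each subject 7 days after the last dose. The start does not. Read literally, criterion 6 attaches its two-part barrier rule only to the days after the last dose, which in the multiple-dose cohort leaves out the run of daily doses up to Day 6. Section 5.3 covers those days with a looser rule. No count is possible: the documents give neither the number of women screened nor their contraceptive use.

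**Whether another criterion settles it.** Criterion 8 asks only that subjects be "willing and able to comply with all scheduled visits, treatment plan, laboratory tests, dietary restrictions, and other study procedures". Exclusion 11 refers to medically acceptable contraception. Neither gives a duration or a number of barriers.

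**The case against.** The strongest reply is that this is a floor plus a more specific rule. Section 5.3 is as much protocol text as 5.1, and a man who follows 5.3 also meets criterion 6. The gap does harm only at a site that reads the criteria in isolation. The consent form, which may carry the full instruction, is not in the reviewed copy.

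Most of that stands, and it is why the point is minor. It does not remove the mismatch. The stricter elements are split between the two sections, so neither can be used alone. Nor are post-study commitments foreign to the eligibility lists: exclusion 18 already carries a 30-day ban on blood and plasma donation after study procedures end.

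Three stronger readings are tempting and not supported.

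- A reader might infer that a hormonal user relying on a condom with spermicide is ineligible. That depends on whether the slash in criterion 6 means and or or. The sentence also governs conduct she agrees to after dosing, not her current practice. She fails only if she declines to add what criterion 6 requires.
- A reader might infer that criterion 6 governs and that its hormonal-user sentence can simply be copied into 5.3. That would lose the whole-study period and weaken cover on dosing days.
- A reader might infer that criterion 3 ("No ingestion of prescription or over-the-counter medications") bars women on oral contraceptives. Criterion 6 plainly provides for hormonal users, so this is at most a side clarification.

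**Conclusion.** The two sections conflict, and the conflict should be removed, as a minor correction. For men in the 5.3 subgroup, criterion 6 falls 23 days short of 5.3, all after the last contraception check, with between 0 and 17 men concerned (0 to 23 with backups). For hormonal users, criterion 6 is stricter on barriers and 5.3 on period. Criterion 6 also covers women who cannot conceive and men with a confirmed vasectomy, whom 5.3 leaves out.

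No endpoint, sample size or analysis is affected. Following the stricter element of each section satisfies both. A reader might infer that men were in fact wrongly instructed, or that a fetal risk through male subjects has been shown. The documents support neither: the consent form was not available, and no such risk is quantified.

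The conclusion assumes that the partner condition in 5.3 applies both to men without a vasectomy and to men with an unconfirmed one. If it applies only to the latter, the subgroup is larger, but the 23 days and the outer range are unchanged.

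**What to change.** Reword criterion 6 so that it matches 5.3 on coverage, start and end:

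- Women of childbearing potential: from at least 4 weeks before the first dose until 7 days after the last.
- Men in the 5.3 subgroup: from the first dose until 30 days after the last.
- Women who cannot become pregnant and men with a confirmed vasectomy: exempt.
- Men whose partners already use a highly effective method: say explicitly that the partner's method suffices, as 5.3 implies, so that an unstated 7-day rule does not linger for them.

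State one barrier rule for hormonal users in both places, running throughout dosing and until 7 days after the last dose. By default use criterion 6's condom/spermicide plus a further barrier, and spell out what the slash means. If the sponsor prefers the looser rule, it should be changed in both sections together.

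The cost is wording only: a protocol amendment with IRB review, and matching consent text if the consent form repeats these rules. Visits, samples and analyses do not change.
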